9.3.3. Covariates and other population characteristics

Characteristics of the study population that are to be described will include calendar year of delivery, maternal age at conception, parity (number of live and still births prior to the on-study pregnancy); indication for AED use, marital/cohabiting status; pregravid body mass index (BMI) as recorded at the first antenatal visit or via a hospital diagnosis of obesity; smoking during pregnancy as recorded at the first antenatal visit; single or multiple gestation; Caesarean delivery; and child's sex. Caesarean delivery and child's sex will be reported but will not be used for adjustment. Indication for gabapentin (and other AEDs) use in 12-months pre-LMP (epilepsy, neuropathic pain, 'other' indications) will be reported

descriptively but will not be used for adjustment as administrative data available for this study have low sensitivity in identifying relevant indications for all pregnancies.

[figure not shown]
The covariates to be included in the propensity-score model are:

- calendar year of delivery;
- maternal age in years at conception;
- marital/cohabiting status;
- smoking during pregnancy;
- obesity (BMI \geq 30 kg/m²) or a hospital diagnosis of obesity;
- single or multiple gestation;
- hospital-recorded morbidity based on inpatient and outpatient specialist care or proxy medication use in 12 months pre-LMP: migraine or other headache syndromes, other neurologic disorders, depression, bipolar disorder, alcohol abuse or dependence, drug abuse or dependence, hypertension, haematological diseases, diabetes, asthma, liver diseases, renal impairment, rheumatic diseases, obesity, disorders of female pelvic organs/genital tract, thyroid disorders, infections (infections will be assessed in 90 days pre-LMP). In Finland, in addition to the hospital diagnoses, diagnoses from primary care are also available and will be used;
- indicators of maternal health care utilisation in the 12 months pre-LMP (number of inpatient and specialised outpatient encounters);

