- for the outcome congenital malformations: maternal medication use each as a dichotomous variable, defined by at least one dispensing during the first trimester (AEDs, antidepressants, hypnotics, antipsychotics, analgesics, antihypertensives, non-steroidal anti-inflammatory drugs, drugs for peptic ulcer/gastroesophageal reflux, folic acid, drugs for in-vitro fertilization, thyroid hormones, systemic corticosteroids, and anti-infectives for systemic use);
- for the outcomes other than congenital malformations: maternal medication use each as a dichotomous variable, defined by at least one dispensing during any trimester (AEDs, antidepressants, hypnotics, antipsychotics, analgesics, antihypertensives, non-steroidal anti-inflammatory drugs, drugs for peptic ulcer/gastroesophageal reflux, folic acid, drugs for in-vitro fertilization, thyroid hormones, systemic corticosteroids, and anti-infectives for systemic use).

[figure not shown]
Full list of the study variables and their operational definitions are provided in [Annex 3](#).

Figure 2. Examples of follow up period for neurodevelopmental outcomes during the study period

[figure not shown]
1.

2.

3.

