9.7. Data analysis

For all data analyses, the birth (not the patient/mother) will be the unit of analysis. Given that a woman could have more than one birth during the study period, data analyses will account for correlated observations using GEE (generalized estimating equation) or robust variance estimates. All steps of the country-specific data analyses will be conducted separately in each participating country according to the description below. Each country will generate a set of identical analytic tables. Registry data will not be provided for very low numbers (less than 5 events) due to data security and data confidentiality rules.

After conducting the country-specific data analyses, country-specific datasets containing crude and adjusted estimates of association will be transferred to Aarhus University Hospital, Denmark, for meta-analyses.

Given that gabapentin has several indications and that administrative data available for this study have low sensitivity in identifying relevant indications for all pregnancies, in this study pregnancies exposed to gabapentin will be compared with pregnancies exposed to medications with similar sets of indications. Because confounding by indication or severity

of indication may persist even against an active comparator,⁷ the amount of confounding may be inferred indirectly by examining whether estimates of association differ depending on the comparator. Here, pregabalin and lamotrigine, which are both indicated for epilepsy, have been identified as suitable active comparators.

In a 2019 publication from Sweden, all individuals aged 15 years or older and being dispensed at least 2 prescriptions of gabapentin in the period 2006-2013 were identified (N=85,360).⁴⁹ The indication of use (i.e. health status before start of treatment) was 6.4% epilepsy, 20% psychiatric disorders, and 52.1% musculoskeletal disorders. In the same publication, the indication of use for pregabalin (n=120,664) was 5.4% epilepsy, 40.9% psychiatric disorders, and 46.2% musculoskeletal disorders. Published data on the most common gabapentin indication in pregnant women are unavailable at this time.

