11. Any-trimester gabapentin (monotherapy or polytherapy) vs. any-trimester lamotrigine (monotherapy or polytherapy)
12. Any-trimester gabapentin (monotherapy or polytherapy) vs. any-trimester pregabalin or lamotrigine (monotherapy or polytherapy)
13. Any-trimester gabapentin (monotherapy only) vs. unexposed to AEDs

14. Any-trimester gabapentin (monotherapy only) vs. any-trimester pregabalin (monotherapy only)
15. Any-trimester gabapentin (monotherapy only) vs. any-trimester lamotrigine (monotherapy only)
16. Any-trimester gabapentin (monotherapy only) vs. any-trimester pregabalin or lamotrigine (monotherapy only)

After estimation of each PS, the following steps will be taken in each country:

- a graph showing distribution of PS of the exposed and unexposed pregnancies will be produced and pregnancies with PS in non-overlapping areas will be deleted (trimming).
- based on the trimmed distributions, strata of PS will be defined using boundaries of the gabapentin-exposed pregnancies. Number of strata will be determined by the number of exposed pregnancies and will vary across countries.
- all exposed and unexposed pregnancies included in a given PS estimation will be classified into these strata based on their PS.
- A weight will be assigned to each unexposed pregnancy based on its stratum; each exposed pregnancy will be assigned the weight of 1.
- A weighted regression analysis will be performed, in which adjusted prevalence ratios or adjusted hazards ratios are estimated using a weighted regression model.

Balance of the covariates following trimming and stratifications-strata specific weights will be assessed in each country's dataset using standardised mean differences. Covariates with standardised mean differences <0.1 will be considered balanced. Initially only first-order variables will be entered into the PS models; if imbalance persists, use of interaction terms may be considered. PS will be estimated by an analyst in each country and the final PS models that achieve acceptable covariate balance may be different in each country.

The crude and the adjusted country-specific estimates of association will be reported separately and combined in a meta-analysis (described in [Section 9.7.7](#)).

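### The propensity-score list in 9.3.3 names neither opioids, anxiolytics nor anxiety disorders, so the balance check as written would not show imbalance in them

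*Protocol*

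**What the plan says.** Section 9.3.3 (Covariates and other population characteristics) fixes the covariates for every propensity score. For malformations, co-medication enters as "maternal medication use each as a dichotomous variable, defined by at least one dispensing during the first trimester". The same classes, with an any-trimester window, serve the other outcomes. There are 13 classes, beginning "AEDs, antidepressants, hypnotics, antipsychotics, analgesics, antihypertensives, non-steroidal anti-inflammatory drugs, drugs for peptic ulcer/gastroesophageal reflux". Analgesics are one class and NSAIDs another. Opioids and anxiolytics are not named.

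The morbidity list for the 12 months before LMP includes "migraine or other headache syndromes, other neurologic disorders, depression, bipolar disorder, alcohol abuse or dependence, drug abuse or dependence" and further conditions such as rheumatic diseases. Anxiety disorders are not among them. Indication for AED use is described, but it "will not be used for adjustment as administrative data available for this study have low sensitivity".

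Section 9.7.3.1 sets the balance rule: "Covariates with standardised mean differences <0.1 will be considered balanced".

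Section 9.7 cites a Swedish study of users aged 15 or older. For gabapentin the mix was "6.4% epilepsy, 20% psychiatric disorders, and 52.1% musculoskeletal disorders". In the same source, "the indication of use for pregabalin (n=120,664) was 5.4% epilepsy, 40.9% psychiatric disorders, and 46.2% musculoskeletal disorders".

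**The concern.** Because indication stays out of the model, the morbidity and co-medication terms have to carry the control for pain and psychiatric background. The list is coarse in both places. One analgesics indicator can be balanced while the kind of analgesic differs between groups. Anxiety and its drug treatment have no term of their own, although psychiatric disorders are about twice as common among the cited pregabalin users as among the gabapentin users.

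The balance table cannot repair this. It tests the covariates in the model, so a pooled variable can pass while its parts differ, and an unlisted variable is not tested.

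Section 9.7 also proposes to judge the amount of confounding from how the estimates differ between comparators. If anxiety raises the risk of an outcome and is more common in the pregabalin group, the gabapentin-pregabalin ratio is pulled down. A ratio near 1 there could then be read as reassurance when part of it is confounding.

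**Working it through.** The protocol states no figure on this point, so there is none to reproduce. Its only relevant numbers are the indication shares in section 9.7. The checks are whether the balance rule could miss an imbalance, and how large an effect could follow under stated assumptions.

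**1. Crude psychiatric gap, gabapentin against pregabalin (protocol figures).**
SMD = (p1 − p0) / √{[p1(1 − p1) + p0(1 − p0)] / 2}.
- Psychiatric, 0.20 vs 0.409: −0.209 / √[(0.160 + 0.2417)/2] = −0.209 / 0.448 = −0.47. That is more than four times the 0.1 limit.
- Musculoskeletal, 0.521 vs 0.462: 0.059 / 0.499 = 0.12.

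**2. Can a pooled class pass while a component is unbalanced? (assumed shares)**
Let any analgesic use be equal in both groups, so the pooled SMD is 0. Let opioids make up 60% of analgesic users in one group and 40% in the other.
- Analgesic use 20%: opioids 0.12 vs 0.08, SMD 0.13.
- Analgesic use 60%: opioids 0.36 vs 0.24, SMD 0.26.

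Both exceed 0.1 while the pooled variable shows no difference.

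**3. Ceiling for the psychiatric gap in the pregabalin contrast.**
Bias factor = [1 + p1(RR − 1)] / [1 + p0(RR − 1)], with p1 = 0.20 and p0 = 0.409 from section 9.7. RR, the confounder-outcome ratio, is assumed.
- RR 1.3: 1.060 / 1.1227 = 0.944.
- RR 1.5: 1.100 / 1.2045 = 0.913.

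This treats the whole psychiatric gap as unadjusted. The score contains several psychiatric terms, so the factor left over should lie nearer to 1.

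**4. Opioids (all inputs assumed).**
Suppose that, among analgesic users, 40% to 60% of gabapentin births and 10% to 20% of comparator births have an opioid, with RR 1.3 to 1.5.
- Among analgesic users: lowest (0.4 vs 0.2, RR 1.3) 1.12 / 1.06 = 1.06; highest (0.6 vs 0.1, RR 1.5) 1.30 / 1.05 = 1.24.
- In the whole cohort the shares must be multiplied by the proportion using any analgesic, assumed 20% to 60% in both groups. Lowest (0.08 vs 0.04, RR 1.3): 1.024 / 1.012 = 1.01. Highest (0.36 vs 0.06, RR 1.5): 1.18 / 1.03 = 1.15.

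The whole-cohort range, 1.01 to 1.15, is the one that bears on the study's ratios.

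**The case against.** The best answer is that the codes are not in view. Section 9.3.3 refers to Annex 3 for operational definitions, and section 9.7.3.1 builds the score from both. The annex might split analgesics, place anxiolytics under hypnotics, or include anxiety. General anxiety disorder stands in the abbreviation list without being used in the text at hand. This stands: one can say only that 9.3.3 does not name these variables, not that the analysis will omit them.

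Second, there is proxy control. The score holds depression, bipolar disorder, alcohol and drug abuse or dependence, antidepressants, antipsychotics, hypnotics, rheumatic diseases, NSAIDs as a separate class, and encounter counts. Listed morbidities may also be identified through medication. This reduces the concern but does not remove it, since none of these measures anxiety or opioid use directly.

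Third, sections 9.7 and 9.9 admit that confounding by indication may persist, and 9.9 says that going beyond yes/no coding for co-medication is infeasible. The admission is fair, but splitting a class keeps yes/no coding. It would not separate a single opioid dispensing from repeated ones.

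A reader might go further and infer that opioids and anxiolytics are the main co-treatments, and that the ratios against AED-unexposed and lamotrigine births are therefore biased upwards. The documents do not support that. They give no co-medication frequencies, no indication mix for lamotrigine and no effect of opioids or sedatives on any outcome. The Swedish figures are not from pregnancies, and section 9.7 says that data on gabapentin's most common indication in pregnant women are unavailable. Musculoskeletal shares are also close for gabapentin and pregabalin, which gives little ground for a large opioid gap in that contrast.

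**Conclusion.** The point holds as a gap in the stated covariate list and in what the balance check can show. It does not establish that the results will be biased. It is best supported for the pregabalin contrast, where the protocol's own figures show a psychiatric gap of SMD about 0.47 and indication is left out of the model.

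The size of any residual confounding cannot be found from the documents. For the cited shares and an assumed ratio of 1.3 to 1.5, the ceiling is a factor of 0.94 to 0.91 on the gabapentin-pregabalin ratio. That assumes the Swedish shares carry over to pregnancies, that the confounder raises risk, and that nothing in the score captures it. The opioid range of 1.01 to 1.15 rests on assumption throughout and should not be quoted as an expected bias. The correction is cheap and is worth making before the scores are estimated.

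**What to change.** In section 9.3.3, for every propensity score:
- add anxiety disorders to the morbidity list for the 12 months before LMP;
- add a yes/no indicator for anxiolytics;
- replace analgesics by two indicators, opioids and other non-NSAID analgesics;
- include all of these in the SMD table of every country.

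If Annex 3 already defines the variables this way, it is enough to align 9.3.3 with it.

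The cost is a few more indicators. Table 2 (section 9.4) shows maternal dispensings held by ATC code, and morbidity by ICD-10 code with ATC proxies, in all four countries, so no new data source is needed. The terms may be sparse in the smaller countries. The rule in 9.7.3.1 for removing low-prevalence covariates on non-convergence would then apply, and the SMD of any term dropped from the model should still be reported.

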9.4. Data sources

Data sources used to construct the analysis dataset for this study are presented in [Table 2](#). Within each country, records from all registries are linkable at the individual level by a unique national person identifier. For births recorded in the birth registries, a maternal unique identifier is a variable on the record of the offspring, enabling exact linkage between a given offspring and maternal history of medication dispensing or diagnoses before or during pregnancy.

Diagnoses in all countries are registered based on the ICD-10 coding system and accessed through registers as specified in [Table 3](#). Similarly, medications are classified according to the ATC coding system and accessed through prescription registers. The medical birth registers in the included countries furthermore contain similar information on other relevant covariates (calendar year of delivery, maternal age at conception, parity; marital/cohabiting status; pregravid body mass index (BMI); smoking during pregnancy; single or multiple pregnancy; and child's sex.)

Validity of routine data in Nordic national registries has been found to be high in all countries.¹⁷⁻²⁶ In Denmark, positive predictive value of diagnoses of cardiac malformations is 89%.²⁷ For drugs used chronically, there is also high level of agreement between general practitioner and dispensing records.²⁸ An agreement between dispensing records and drug use reported in the standard medical antenatal records included in the birth register was 69% for antiepileptics in Sweden.²⁹

Table 2. National registries in Denmark, Finland, Norway and Sweden and type of data available from each registry

Study variable/role	Type of data	Data source(s)	Coding system(s) used
Person identification (mothers and children)	Unique personal identifier for data linkage	Danish Civil Registration System ³⁰ Danish Civil Registration System ³⁰ Finnish Medical Birth Register* National Registry of Norway Swedish Total Population Register ³¹	N/A
Study population	Pregnancies ending in singleton/multiple live birth or stillbirth	Danish Medical Birth Registry ²⁶ Finnish Medical Birth Register* ²⁶ Medical Birth Registry of Norway ²⁶ Swedish Medical Birth Register ²⁶	A specific variable in each birth registry
	Pregnancies ending in therapeutic 2nd trimester induced abortion	Danish National Patient Registry ^{32,33} Finnish Register on Induced Abortions* Norwegian Register of Pregnancy Terminations (part of the Medical Birth Registry of Norway) Not available in Sweden	ICD-10

Table 2. National registries in Denmark, Finland, Norway and Sweden and type of data available from each registry

Study variable/role	Type of data	Data source(s)	Coding system(s) used
Exposure (for full list see Section 9.3.1)	Maternal dispensings of gabapentin, pregabalin, lamotrigine	Danish National Prescription Registry ³⁴ Finnish Prescription Register ³⁵ Norwegian Prescription Database ³⁵ Swedish Prescribed Drug Register ³⁵	ATC
Outcome (for full list see Section 9.3.2)	Major congenital malformations	Danish Medical Birth Registry (stillbirths)/ Danish National Patient Registry (livebirths/induced abortions) Finnish Medical Birth Register* Finnish Register of Congenital Malformations* Finnish Register on Induced Abortions* Finnish Care Register for Health Care Medical Birth Registry of Norway Swedish Medical Birth Register Swedish National Patient Register	ICD-10, local codes (Denmark)
	Birth weight, gestational age, Apgar score at 5 minutes, head circumference, stillbirth	Danish Medical Birth Registry Finnish Medical Birth Register* Medical Birth Registry of Norway Swedish Medical Birth Register	A specific variable in each birth registry
	Neurodevelopmental outcomes	Danish National Patient Registry ³² Danish Psychiatric Central Research Register ³⁶ Danish Psychiatric Central Register Finnish Care Register for Health Care Finnish Register of Primary Health Care visits Norwegian Patient Registry ^{37,38±} Swedish National Patient Register ^{22,39} Danish National Prescription Registry ³⁴ Finnish Prescription Register ³⁵ Norwegian Prescription Database ³⁵ Swedish Prescribed Drug Register ³⁵	ICD-10 for diagnoses, ATC codes for drug proxies
Characteristic of study population and covariates (for full list see Section 9.3.3)	Mother: age, parity, marital/cohabiting status, mode of delivery, smoking during pregnancy, BMI Offspring: sex, multiplicity of gestation	Danish Medical Birth Registry Finnish Medical Birth Register* National Registry of Norway ⁴⁰ Swedish Medical Birth Register ^{41,42} Swedish National Patient Register	A specific variable in each birth registry

Table 2. National registries in Denmark, Finland, Norway and Sweden and type of data available from each registry

Study variable/role	Type of data	Data source(s)	Coding system(s) used
	Maternal morbidity (including indication for gabapentin) Markers of health care utilisation	Danish National Patient Registry, ³² Finnish Care Register for Health Care Finnish Register of Primary Health Care visits Norwegian Patient Registry ³⁷ Swedish National Patient Register ⁴³ Danish National Prescription Registry ³⁴ FinnishDatabase Finnish Prescription Register ³⁵ Norwegian Prescription Database ³⁵ Swedish Prescribed Drug Register ³⁵	ICD-10 for diagnoses, ATC for medication proxies
	Maternal medications	Danish National Prescription Registry ³⁴ Finnish Prescription Register ³⁵ Norwegian Prescription Database ³⁵ Swedish Prescribed Drug Register ³⁵	ATC
Loss to follow-up	Death, emigration [†]	Danish Civil Danish Civil Registration System ³⁰ Finnish Causes of Death Register Finnish Population Register Centre National Registry of Norway Swedish Cause of Death Register ⁴⁴ Swedish Total Population Register	A specific variable in each registry

*Data for the Medical Birth Register, the Register on Induced Abortions, the Malformation Register and the Prescription Register (3 months before last menstrual period) can be obtained from the Finnish Drugs and Pregnancy Project (DPP) database.

[†]Emigration data not available in the Norwegian dataset

[‡]Data available from 2008 onwards in Norway

9.5. Study size

Table 3 shows estimated number of total pregnancies ending in live or stillbirth and pregnancies with AED exposure (any use, i.e., pregnancies exposed to monotherapy and pregnancies exposed to polytherapy).

Table 3. Estimated numbers of pregnancies ending in live or still birth (any use, i.e., pregnancies exposed to monotherapy and pregnancies exposed to polytherapy)*

	Denmark (2005-2016)	Finland (2005-2016)	Norway (2005-2016)	Sweden (2006-2016)	TOTAL
Live/still births	728,052	701,550	717,219 (657,451)	1,152,002	3,298,823

Table 3. Estimated numbers of pregnancies ending in live or still birth (any use, i.e., pregnancies exposed to monotherapy and pregnancies exposed to polytherapy)*

	Denmark (2005-2016)	Finland (2005-2016)	Norway (2005-2016)	Sweden (2006-2016)	TOTAL
Pregnancies with dispensation of Gabapentin, first trimester	374	374	344	500	1,592
Gabapentin, any time during pregnancy	388	388	467	500	1,743
Pregabalin, first trimester	372	1,020 (935)	248 (227)	1,230	2,870
Pregabalin, any time during pregnancy	377	1,053 (965)	225 (307)	1,275	2,930
Lamotrigine, first trimester	2,266	1,048 (961)	1,841 (1,688)	2,838	7,993
Lamotrigine, any time during pregnancy	2,379	1,104 (1,012)	2,110 (1,934)	2,991	8,584

*Number of exposed in Denmark and Sweden are the actual numbers for 2005-2016; estimated for Finland and Norway based on 2005-2015 data in parenthesis. No exclusion criteria are applied in this table.

The 2005-2016 estimated numbers of pregnancies ending in live or still birth for potentially analysis-relevant categories for Norway and Finland were unavailable at the time of writing the protocol but are estimated using data from 2005-2015 to provide the most conservative estimate.^{14,45,46,47}

Table 4 shows the upper limit of the 95% confidence interval of risk ratio that can be ruled out with 80% probability, for different scenarios with respect to the size of the exposed and comparator groups based on counts provided in Table 3. The study size is estimated at greater than 3,000,000 pregnancies, including approximately 1743 exposed to gabapentin at any time. For example, a study of this size (1743 exposed to gabapentin at any time, 3,298,823 pregnancies in total) will rule out a relative risk with a 95% upper confidence limit of 1.5 with 80% probability, assuming the following: gabapentin vs. ‘unexposed to AEDs’ as comparator, background prevalence of major congenital malformations is 3%; gabapentin exposure prevalence is 0.8%; and the true underlying risk ratio is 1.0 (see Table 4).

Table 4. Upper limits of 95% confidence interval for risk or prevalence ratios depending on the prevalence of selected outcomes representative of prevalence of various study outcomes

Outcome	Estimated prevalence of outcome	Upper limit of 95% confidence interval for risk ratio can be ruled out with at least 80% probability (based on actual or estimated frequencies; approximate the analysis with gabapentin-unexposed as a comparator*)
Malformations of the nervous system ^{14,35} , mental retardation	0.2%	4.801 (use first-trimester counts)
Stillbirth, postnatal outcomes, ASD	0.6%	2.373 (use any time during pregnancy counts)
Cardiac congenital malformations, postnatal outcomes ^{12,14} , ADHD	1%	1.950 (use any time during pregnancy counts)
Any major congenital malformation ^{12,14}	3%	1.465 (use any time during pregnancy counts)
Preterm birth/SGA	10%	1.223 (use any time during pregnancy counts)
Upper limit of 95% confidence interval for risk ratio can be ruled out with at least 80% probability (based on actual or estimated frequencies; approximate the analysis with gabapentin-pregabalin as a comparator*)		
Malformations of the nervous system ^{14,35} , mental retardation	0.2%	7.069 (use first-trimester counts)
Stillbirth, postnatal outcomes, ASD	0.6%	2.977 (use any time during pregnancy counts)
Cardiac congenital malformations, postnatal outcomes ^{12,14} , ADHD	1%	2.324 (use any time during pregnancy counts)
Any major congenital malformation ^{12,14}	3%	1.619 (use any time during pregnancy counts)
Preterm birth/SGA	10%	1.289 (use any time during pregnancy counts)
Upper limit of 95% confidence interval for risk ratio can be ruled out with at least 80% probability (based on actual or estimated frequencies; approximate the analysis with gabapentin-lamotrigine as a comparator*)		
Malformations of the nervous system ^{14,35} , mental retardation	0.2%	5.571 (use first-trimester counts)
Stillbirth, postnatal outcomes, ASD	0.6%	2.579 (use any time during pregnancy counts)
Cardiac congenital malformations, postnatal outcomes ^{12,14} , ADHD	1%	2.080 (use any time during pregnancy counts)
Any major congenital malformation ^{12,14}	3%	1.520 (use any time during pregnancy counts)
Preterm birth/SGA	10%	1.247 (use any time during pregnancy counts)
Upper limit of 95% confidence interval for risk ratio can be ruled out with at least 80% probability (based on actual or estimated frequencies; approximate the analysis with gabapentin-pregabalin or lamotrigine as a comparator*)		
Malformations of the nervous system ^{14,35} , mental retardation	0.2%	5.447 (use first-trimester counts)
Stillbirth, postnatal outcomes, ASD	0.6%	2.547 (use any time counts)
Cardiac congenital malformations, postnatal outcomes ^{12,14} , ADHD	1%	2.060 (use any time counts)
Any major congenital malformation ^{12,14}	3%	1.511 (use any time counts)

Table 4. Upper limits of 95% confidence interval for risk or prevalence ratios depending on the prevalence of selected outcomes representative of prevalence of various study outcomes

Preterm birth/SGA	10%	1.243 (use any time counts)
-------------------	-----	-----------------------------

*Can include exposed to other AEDs i.e., monotherapy or polytherapy; calculations made without applying any exclusion criteria. The computations were done using SAS software based on the ‘Study size’ worksheet of the Episheet.⁴⁸

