9.7.7. Combining results

Crude and adjusted estimates of association from Sweden, Norway, and Finland will be transferred to Aarhus University, Aarhus, Denmark for meta-analyses or other combined analyses. Because of the similarities between the healthcare systems in the Nordic countries and the use of a common study protocol with well-defined selection of exposures, outcomes and covariates, a fixed-effects meta-analysis is justifiable applied.⁵⁵ Country-specific crude and adjusted estimates of association for each prespecified comparison will first be calculated and presented. These results will then be combined in a meta-analysis, or, if deemed more suitable, another method that allows incorporation into combined estimates of associations with no exposed events, such as Mantel-Haenszel pooling methods.⁵⁶ For each outcome the coordinating centre will use the inverse variance method in the fixed effects meta-analyses, which is weighting the country-specific estimates of association by the inverse of the within-country variances. Homogeneity of the estimates will be verified, and a random-effects meta-analysis will be considered as an alternative should the estimates be found to be heterogeneous. The rejected model, i.e. the model not used as the primary model, will be checked in a sensitivity analysis. For example, if the fixed-effect model is used as the primary meta-analytical approach, the random-effects model will be checked in a sensitivity analysis, and vice versa. Results of combined analyses will be presented using a standard forest plot, reporting the country-specific overall crude and adjusted point estimates, and the pooled overall crude and adjusted point estimates, all with 95% CIs.

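### Table 4's pregabalin limits come from the collapsed four-country totals; under the planned country-stratified analysis they are met with about 76–77% probability, not at least 80%

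*Protocol*

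**What the plan says.** Section 9.5 introduces the table thus: "Table 4 shows the upper limit of the 95% confidence interval of risk ratio that can be ruled out with 80% probability". Each block is headed "Upper limit of 95% confidence interval for risk ratio can be ruled out with at least 80% probability". The worked example, against births unexposed to AEDs, assumes that "the true underlying risk ratio is 1.0". In the pregabalin block the limits are 7.069 (outcome prevalence 0.2%, first-trimester counts) and, on any-time counts, 2.977 (0.6%), 2.324 (1%), 1.619 (3%) and 1.289 (10%). The 3% row, for any major malformation, reads "1.619 (use any time during pregnancy counts". The footnote says that polytherapy can be included, that no exclusions were applied, and that the Episheet study-size worksheet was the basis.

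On the analysis, section 9.7 says: "All steps of the country-specific data analyses will be conducted separately in each participating country". Section 9.6 keeps patient-level data from Finland, Norway and Sweden away from the coordinating institution. Section 9.7.7 says: "For each outcome the coordinating centre will use the inverse variance method in the fixed effects meta-analyses". It allows another method, such as Mantel-Haenszel, where there are no exposed events.

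**The concern.** A limit computed from one collapsed table describes an analysis that the plan does not run. If the two drugs were used in the same proportion in every country, the difference would not matter. Table 3 shows that they were not. Any time in pregnancy, the gabapentin:pregabalin counts are 388:377 in Denmark, 388:1,053 in Finland, 467:225 in Norway and 500:1,275 in Sweden. Comparing only within country then discards information that the collapsed table counts, so the error runs against a probability stated as a floor. Section 9.9 relies on exposed reference groups to reduce confounding by indication, so the precision claimed against pregabalin will be read when that comparison is interpreted.

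**Working it through.** **Inputs.** Table 3, in the order Denmark, Finland, Norway, Sweden, total.
- Gabapentin: "Gabapentin, first trimester 374 374 344 500 1,592" and "Gabapentin, any time during pregnancy 388 388 467 500 1,743".
- Pregabalin, first trimester: 372, 1,020, 248, 1,230; total 2,870.
- Pregabalin, any time: 377, 1,053, 225, 1,275; total 2,930.
- True ratio 1. It is stated for the unexposed example and assumed here, and the pregabalin limits reproduce with it.

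**Step 1: the printed limits.** Let I be the information term and p the prevalence. Then SE = sqrt[((1−p)/p)/I] and the limit is exp(2.8016 × SE), where 2.8016 = 1.9600 + 0.8416. For one collapsed table I = n1·n0/(n1+n0).
- Any time: 1,743 × 2,930/4,673 = 1,092.9.
- First trimester: 1,592 × 2,870/4,462 = 1,024.0.
- At 3%: SE = sqrt(32.333/1,092.9) = 0.1720 and the limit is 1.619, as printed. The other four rows reproduce in the same way, to rounding.

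**Step 2: stratify by country.** With a common prevalence and a true ratio of 1, I becomes the sum over countries of n1·n0/(n1+n0).
- Any time: 191.2 + 283.5 + 151.8 + 359.2 = 985.7, which is 90.2% of 1,092.9.
- First trimester: 186.5 + 273.7 + 144.1 + 355.5 = 959.8, which is 93.7% of 1,024.0.

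**Step 3: probability of meeting the printed limits**, Φ(ln(limit)/SE − 1.96). At 3%, SE = sqrt(32.333/985.7) = 0.1811 and Φ(0.4818/0.1811 − 1.96) = 75.8%.

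| Prevalence | Printed limit | Probability, stratified | Limit at 80%, same counts | Simulated Mantel-Haenszel |
|---|---|---|---|---|
| 0.2% (first trimester) | 7.069 | 77.4% | 7.54 | 71.3% |
| 0.6% (any time) | 2.977 | 75.8% | 3.15 | 76.4% |
| 1% (any time) | 2.324 | 75.8% | 2.43 | 76.6% |
| 3% (any time) | 1.619 | 75.8% | 1.66 | 76.7% |
| 10% (any time) | 1.289 | 75.7% | 1.31 | 76.4% |

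The simulation drew binomial counts by country at equal prevalence in both groups.

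**Step 4: the 0.2% row.** Expected events are 1,592 × 0.002 = 3.2 and 2,870 × 0.002 = 5.7. A single collapsed table, simulated, also reaches only about 73%. Stratification therefore explains about 2 points of the simulated shortfall; the rest is sparse events. Counting replicates with no gabapentin events as successes raises the Mantel-Haenszel figure to 75.5%.

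**Step 5: the Norwegian entry.** Any-time pregabalin in Norway is printed as 225, with 307 in parentheses for the shorter period. The longer period cannot hold fewer births, and an any-time count cannot be below the first-trimester count of 248. Scaling 307 by 717,219/657,451 gives 335. Then I is 1,029.0 stratified against 1,107.8 collapsed (92.9%, a 7% loss), and the any-time rows give 77.5–77.6%.

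**Step 6: exposure window.** Malformations are analysed by first-trimester exposure (section 9.7.4.2), but the 1% and 3% rows use any-time counts. First-trimester counts give, collapsed, 1.645 at 3%. Stratified, they give 1.67 at 3% and 2.46 at 1%.

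**Step 7: other blocks, stratified.** AED-unexposed 80.0%; lamotrigine 79.5–79.6%; pregabalin or lamotrigine, with the two drug counts summed, 80.3–80.6%.

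**The case against.** The block header calls the figures approximate and based on actual or estimated frequencies, and the footnote admits that no exclusions were applied. Part of the any-time loss comes from a doubtful Norwegian count. The study takes all registry births in fixed periods, so no enrolment target, test or stopping decision uses Table 4. The narrative cites only the AED-unexposed limit, which stratification leaves intact. The shifts are small, for example 1.619 to 1.66 at 3%.

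The points on size and consequence stand, and they make this minor. The disclosure point does not: neither header nor footnote says that country structure was ignored, and the header still states a floor. Correcting Norway narrows the gap without closing it.

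Two stronger readings are not supported. A reader might infer that stratification takes the block down to 71%; that figure belongs to the 0.2% row alone and is mostly sparse events. A reader might also infer that the inverse-variance default collapses in the rare-outcome rows. That depends on dropping countries with a zero cell, and section 9.7.7 provides for another method where there are no exposed events.

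**Conclusion.** The stated probability is wrong for the pregabalin block. On the protocol's own formula and counts, the planned stratified analysis meets the printed limits with 75.7–77.4% probability, 2.6 to 4.3 points below the floor. With Norway at 335 the any-time rows give about 77.5%, and with first-trimester counts the printed 1.619 is met with about 75%. The 0.2% row is about 71% by simulation, for a largely separate reason. These figures assume a common prevalence, a true ratio of 1 and all counts available. Propensity-score trimming, weighting and exclusions are left out. The finding is confined to this block and does not show that the study as a whole is too small. Severity: minor.

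**What to change.** 1. Reconcile the Norwegian any-time pregabalin entry, 225 (307), in Table 3 and its total of 2,930.
2. Recompute the pregabalin block from the country counts with the country-stratified estimator.
   - Malformation outcomes, first-trimester counts: about 1.67 at 3% (any malformation) and 2.46 at 1% (cardiac).
   - Other outcomes, any-time counts: about 3.15 at 0.6%, 2.43 at 1% (ADHD) and 1.31 at 10%; with Norway at 335, about 3.08, 2.39 and 1.30.
3. Give an exact or simulated value for the 0.2% row.

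Alternatively, keep the printed limits and restate the probability as about 75–78%, and about 71% for the 0.2% row. Either route needs a few lines of code and new table entries. Data and design do not change; the stated precision becomes slightly less favourable.
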